Meal test. At study visits 1, 3 and 4 (0, 18 and 36 wk), subjects will have an OGTT (900-1100 AM) in the fasting condition, followed at study visits 0 and 36 wk by a standardized mixed meal caloric preload (macaroni & cheese at 1100 AM) and a free buffet meal (at 1230 PM). The buffet meal is an objective measure of satiety as it assesses food intake and choice after a caloric preload. The standardized test meal preload will provide 12% of estimated daily caloric requirements,⁸¹ based on the Schofield-HW equation.⁸² The purpose of the test meal is to ensure that study participants are in an equally fed state (together with oral glucose, total preload will be 22-27% of estimated daily caloric intake). Ninety minutes later, an ad libitum buffet meal will be served consisting of a wide variety of food items and more than the child's estimated daily calorie requirements will be offered (5,000 kcal). Participants will have access to the buffet for 30 min, after which calorie intake and composition of consumed foods will be measured by weighing back uneaten food. Hunger and fullness will be assessed every 30 min from fasting state before starting the OGTT until the end of the buffet meal using visual analog scales (VAS)⁸³ to assess subjective appetite, reliable in children over age 7 y,⁸⁴ and used by us previously.⁸⁵

Metabolic outcomes. Blood glucose, insulin, lipid panel, hemoglobin A1c, and as a measure of low-grade inflammation C-reactive protein will be assessed by high-sensitive (hsCRP) testing at a central lab (Northwest Lipid Research Laboratories, Seattle). Glucose tolerance will be assessed by a 2-hour oral glucose tolerance test. After placement of an intravenous catheter (IV), a baseline blood sample will be collected for measurement of hemoglobin A1C, and insulin (processed by the central lab). A 2-h OGTT (1.75 g/kg Glucola [maximum 75 g]) will then be performed with sample collection at 0', 30', 60', 90' and 120' for measurement of glucose and insulin. Samples will be placed on ice, and will be centrifuged. Leptin, total adiponectin, α -MSH, and soluble leptin receptor (sOB-R) are potential indicators of leptin sensitivity,⁸⁶⁻⁸⁹ and will be assessed in fasting state (leptin, total adiponectin, and sOB-R, R&D Systems, Minneapolis, MN; α -MSH, Phoenix Pharmac., Belmont, CA, the assay cross

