Treatment dosage and duration are based on prescribing information and prior successful clinical trial weight loss results.^{31,110} The placebo-control group is an essential arm in this trial as study measures can change over time without drug intervention and it supports the evaluation of efficacy and safety. The drug and placebo kits will be supplied by AstraZeneca, or the current pharmacologic company responsible for ExQW. Exenatide vials or pens 2.0 mg powder for injection will be supplied. All subjects will have weekly phone calls when not coming for a study visit, to check adherence and any potential

adverse effects. Any evidence for adverse effects will be discussed with the PI of each site and safety clinical visits will be considered.

All study medication will be stored/locked in the investigational pharmacy under appropriate temperature conditions. Dispensing and accountability records will be maintained by appropriate staff members.

Analysis

Analysis plan and sample size calculations by Aim.

The research team includes personnel with statistical and data management expertise for overseeing data collection, storage methods, and the following analyses (see letter of support, [name]). Adherence data collected during the placebo run-in phase will be summarized descriptively. All subjects completing the run-in phase will go on to the randomized treatment phase. The primary analyses will use the intention-to-treat (ITT) approach; i.e., subjects will be analyzed according to their randomized assignment regardless of treatment received. In addition, data of all completers will be analyzed separately as a sensitivity analysis. While every attempt will be made to collect complete data and retain all subjects, all sample size and power calculations account for dropout. Statistical methods have been selected to allow for inclusion of partial data. All testing is two-sided and $\alpha=0.05$. Repeated measures analyses will be conducted using SAS (SAS Institute, Inc., Cary, NC, USA) or R (The R Foundation for

Statistical Computing).

Analysis populations: All eligible subjects randomized will be included in the ITT population. The ITT population will be the primary analysis population for all primary, secondary, and tertiary outcomes. The safety population will be the primary population for all safety analyses, and include all subjects who receive at least one dose of study drug or placebo.

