Table 1. Summary of Study Measures and Outcomes and Their Use in the Proposed Research

Measure	Domain	Instrument	Aim	Role/Application
$\Delta\text{BMI}\%$	Adiposity	Anthropometry	1	Primary outcome
Total body fat mass	Body composition	DEXA	1	Secondary outcome
Fat and total calorie intake	Post test meal satiety assessment	Free buffet meal analysis	1	Secondary outcome
Glucose tolerance	Glucose tolerance, MetS	Glucose at 0', 120' (OGTT)	2	Secondary outcome
HDL, triglycerides	MetS	Fasting lipids	2	Secondary outcome
hsCRP	Inflammation	hsCRP at fasting time point	2	Secondary outcome
Free living EE	Energy homeostasis	Doubly labeled water	3	Tertiary outcome
Energy intake	Energy intake	24h dietary recall (ASA24)	3	Tertiary outcome
Leptin, adiponectin, sOB-R, α -MSH, HOMA-IR, WBISI	Energy homeostasis, leptin sensitivity, and insulin resistance	Baseline and stimulated hormones	3	Tertiary outcomes and predictors

Aim 1: To test effects of GLP1RA on hypothalamic obesity prospectively.

Sample: Available anthropometry measures will be included in the analyses (see also Fig. 1 below).

Primary outcome analysis: For efficacy analysis the primary outcome is % change in BMI from week 0 (baseline) to 36 wk. A piecewise (separating the randomized and run out phases) linear mixed-effects model¹¹¹ will be fit with % change in BMI from baseline to 36 wk as the outcome; treatment, time, and the interaction between treatment and time as factors of interest; and randomization stratification variables (site, age, and gender) included as covariates. This model is a generalization of analysis of covariance (ANCOVA) that allows all follow-up repeated measures to be included.

Table 2. Additional Descriptive Parameters, Predictors and Covariates used in Study

Measure	Domain	Instrument	Aim
ΔBMI , ΔBMI z-score	Adiposity	Anthropometry	1
Subjective appetite	Hunger and fullness rating	Visual analog scale	1
Syst. & diast. BP	CVD risk factor, MetS	Ambulatory BP	2
Exercise	Physical activity measure	Actigraphy ^{112,113}	3
Energy intake	Energy intake	24h dietary recall	3
Eating behavior	Assessment of overeating and food reward	Overeating (CEBQ), ⁷⁶ & hyperphagia. ⁷⁷	3
Brain lesion score, hypothalamic region and residual lesion volumes	Structural lesion in the pituitary-hypothalamic area	Brain MRI images	3

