between treatment and time will be used to specifically test for a significant difference in % change in BMI from baseline to 36 wk post-treatment and 54 wk (end of open label extension). Additionally, descriptive summaries will be prepared for change in BMI z-score to supplement interpretation of findings. Study outcomes, their use, and descriptive parameters are in Tables 1 & 2.

Table 3 Aim	Outcome	Observed Δ Exenatide vs. Control	Observed pooled Std. Dev.	Observed relative effect size
1	% ΔBMI	-4.29	3.84	-1.12
1	Absolute ΔBMI	-1.74	1.25	-1.39
2	$\Delta\text{Glucose AUC}$ (per 100)	-29.36	26.44	-1.11
2	$\Delta\text{Insulin}$ (mU/L)	-7.62	7.14	-1.07

Sample size and power: Table 3 shows observed relative effect sizes in our preliminary study for the between-treatment comparison of change from baseline to 3 mo (data from previous study²²). Assuming a normal distribution of changes, a type I error rate of 0.05, and a dropout rate of up to 20%, a sample size of 24 subjects per group (19 evaluable) will provide 85% power to detect relative treatment effect sizes of 1 or greater (in absolute value) for % change in BMI, which is consistent with the preliminary data.

Expected result: We expect GLP1RA treatment will reduce BMI (primary efficacy endpoint). Further we expect that GLP1RA treatment will reduce total body fat mass and increase satiety (assessed by hunger VAS as well as fat and total calorie intake at free buffet test meal).

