Aim 2: To determine effects of GLP1RA on cardiometabolic risk factors. Secondary outcomes analysis: Secondary outcomes are change in the following metabolic CVD risk factors: blood glucose, triglycerides, HDL cholesterol, and hsCRP. All continuous secondary efficacy endpoints will be analyzed using similar repeated measures analyses to those previously described for the primary outcome to examine differences in the change in secondary outcomes, one at time, from baseline to 36 wk. Histograms will be examined, and if data are markedly skewed right, log transformations will be applied prior to analysis. Measures of insulin resistance and insulin secretion will be compared from baseline to 18 and 36 wk to test whether treatment effects are beneficial during the second half of intervention. Sample size and power: Table 3 shows observed relative effect sizes in our preliminary study for between treatment comparison of change from baseline to 3 mo (dataset from previous study²²). Assuming a normal distribution of changes, a type I error rate of 0.05, and dropout rate of up to 20%, a sample size of 24 subjects per group (19 evaluable) will provide 85% power to detect relative treatment effect sizes of 1 or greater (in absolute value) for changes in cardiometabolic risk factors in patients with HO, which is consistent with the preliminary study.

Expected results and benchmarks for success (secondary efficacy endpoints): We expect that GLP1RA treatment will lead to improved metabolic CVD risk factors (higher HDL; lower blood pressure, blood glucose, hsCRP, and triglycerides).

Aim 3: To explore additional outcome measures, and predictors of treatment responses.

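### Aim 2's changes from baseline to weeks 18 and 36 can show benefit at mid-treatment and end of treatment, but not what weeks 18 to 36 contributed

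*Combined protocol and SAP*

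**What the plan says.** In Section 4, Analysis, Aim 2, the insulin resistance and insulin secretion measures are to be "compared from baseline to 18 and 36 wk to test whether treatment effects are beneficial during the second half of intervention". For the continuous secondary endpoints, the same paragraph calls for repeated measures analyses like the primary one, "to examine differences in the change in secondary outcomes, one at time, from baseline to 36 wk". The primary model has "treatment, time, and the interaction between treatment and time as factors of interest", and the contrasts named for it end at week 36 and week 54.

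The data come from the glucose tolerance tests: "At study visits 1, 3 and 4 (0, 18 and 36 wk), subjects will have an OGTT" (Section 4, Meal test). The visit list in Section 6 agrees.

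The protocol nowhere specifies a week 18-to-36 contrast, a comparison of the two changes with each other, or a rule for drawing one conclusion from the pair.

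On the standing of the measures, Table 1 lists HOMA-IR and WBISI as tertiary, and the paragraph on OGTT-derived measures calls the insulinogenic index (IGI) exploratory. Reduced insulin secretion is nevertheless one of the hypotheses under Specific Aim 2.

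**The concern.** The stated question concerns a period, and both named comparisons start before that period begins. Baseline-to-18 contains none of the second half. Baseline-to-36 contains both halves added together. A treatment effect at week 36 is therefore compatible with an effect that came early and was held, one that built up steadily, one that arose only after week 18, or one that peaked at week 18 and then partly faded.

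At stake is what the report may say about the course of the metabolic effect. Without a specified contrast or decision rule, a significant baseline-to-36 result could be described as a second-half benefit in the sense of further improvement, which it does not establish. The three OGTTs already planned would allow these courses to be estimated separately.

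**Working it through.** **Inputs from the protocol.** 24 per group, 19 evaluable, dropout up to 20%, two-sided alpha 0.05, planning effect of 1 SD of change, stated power 85% (Aim 2, sample size and power); 1:1 allocation (Section 5, Enrollment); OGTT at weeks 0, 18 and 36.

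**Inputs assumed.** Normal data with equal correlation r between any two visits, r = 0.3, 0.5 or 0.7, scaled so that each change has SD 1. Unadjusted two-sample t-tests.

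**1. The plan's own figure.** 24 × 0.80 = 19.2, so 19 evaluable. The noncentrality is 1 × √(19/2) = 3.08 with 36 degrees of freedom, which gives power 85.1% (86.9% by the normal approximation). The stated 85% reproduces.

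**2. What each comparison estimates.** Let D18 and D36 be the between-arm differences in change from baseline, and G the between-arm difference in change from week 18 to week 36. Then D36 = D18 + G, so G = D36 − D18. The plan tests D18 and D36 against zero. It does not test or estimate G.

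**3. How the tests behave under different courses.** Simulation with 20,000 trials per course and 19 per arm; the rows are for r = 0.5. Effects are in SD of change, positive meaning benefit.

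| True D18, D36 | True G | Baseline-to-18 significant | Baseline-to-36 significant | Both | Direct 18-to-36 contrast significant |
|---|---|---|---|---|---|
| 1, 1 (early, held) | 0 | 84.7% | 84.6% | 75.1% | 4.7% |
| 1, 0.7 (partly lost) | −0.3 | 85.1% | 55.9% | 52.2% | 14.2% |
| 1, 0 (fully lost) | −1 | 85.2% | 4.9% | 3.7% | 85.0% |
| 0.5, 1 (steady gain) | +0.5 | 32.2% | 84.9% | 30.9% | 32.3% |
| 0, 1 (late only) | +1 | 4.9% | 84.8% | 3.6% | 84.8% |

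The early, steady and late courses give the same baseline-to-36 result, about 85%, although G is 0, 0.5 and 1. Requiring both comparisons does not help: it favours the early, held course (75%) over the steady (31%) and late (4%) courses.

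For r = 0.3 and 0.7 every figure is within about one percentage point. The reason is that with visit variance s² the two changes have covariance s²(1 − r) and variance 2s²(1 − r), so their correlation is 0.5 whatever r is. Under another correlation structure the 75% would move, roughly between 0.85 × 0.85 = 72% (uncorrelated changes) and 85% (perfectly correlated changes).

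**4. What the direct contrast can deliver.** With 19 per arm its power is 14.7% for G = 0.3, 32.3% for G = 0.5 and 85.1% for G = 1. The half-width of its 95% CI is about 2.03 × √(2/19) = 2.03 × 0.324 = 0.66 SD of the 18-to-36 change.

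**The case against.** The strongest reply is that the sentence asks whether effects are beneficial in the second half, which can describe a state and not an increment. Weeks 18 and 36 are the two ends of that half. Comparing the arms at each, relative to baseline, asks whether benefit is present throughout. On that reading an effect reached by week 18 and held is correctly reported as beneficial, one that fades but stays above zero is too, and the 85% in the first row is power and not error. This stands. The wording allows both readings, and the comparisons suit one of them.

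A reader might go further and infer that the plan would falsely claim second-half benefit in about 89% of trials against a nominal 5%. That figure comes from Table 3's insulin row: 7.62/7.14 = 1.07 SD, with power 89.4% at 19 per arm. The documents do not support this inference:

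- The 5% benchmark presupposes a null of no further gain after week 18, which the protocol never states.
- No rule says that baseline-to-36 alone triggers a claim.
- Table 3 does not identify its insulin row with HOMA-IR, WBISI or IGI. It also does not show that the row carries the BMI-change adjustment described for glucose metabolism parameters.

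A reader might also infer that the preliminary study points to an early plateau. Table 3 reports results only "for the between-treatment comparison of change from baseline to 3 mo", and one time point says nothing about what follows it.

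**Conclusion.** The plan's two comparisons cannot separate further gain, maintenance and waning over weeks 18 to 36, and the sentence does not say whether it means gain or persistence. Under the gain reading, a 1 SD effect reached by week 18 and held gives a significant baseline-to-36 comparison in about 85% of trials, and two significant comparisons in about 75%, with a true second-half effect of zero. Under the persistence reading the comparisons are suitable and only the wording is at fault.

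The figures rest on the planning effect, unadjusted t-tests and an assumed correlation structure. The early, held course is an illustration, not a forecast. If the effect were fully lost by week 36, baseline-to-36 would reject in only about 5% of trials and no such misreading would arise.

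Severity is minor. The primary endpoint, sample size and data collection are untouched, and the insulin indices rank below the secondary outcomes, although the analysis is presented as a test and bears on an Aim 2 hypothesis.

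**What to change.** - State the question. If persistence is meant, say that the aim is to see whether benefit is present at week 18 and still present at week 36.
- In the same repeated-measures model, prespecify the between-arm difference in week-36-minus-week-18 change and report it as an estimate with a 95% CI.
- Let time enter that model by visit, or with a break at week 18. The primary model is described as piecewise between the randomized and open-label phases. A single slope over weeks 0 to 36 would force the 18-to-36 difference to be half of the baseline-to-36 difference.
- Label baseline-to-18 and baseline-to-36 as the effects at mid-treatment and at end of treatment. Claim second-half gain or waning only from the 18-to-36 contrast.
- Do not read a non-significant 18-to-36 contrast as proof of maintenance. With a real gain of 0.3 or 0.5 SD it would be non-significant in about 85% or 68% of trials. Let the interval show what remains possible.

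The cost is one contrast and a few sentences, with no added visits, samples or patients. The price is a wide interval for the new estimate.

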Physical activity. In one of our prior studies with CP patients, we assessed physical activity by accelerometry.⁵⁴ In the proposed study, subjects' physical activity will be measured by the Actigraph GT3M accelerometer, worn on the non-dominant wrist. To measure activity and sleep duration, subjects will wear the actigraph monitor continuously for 2 wk. Drs. Roth⁵⁴ and [name] have used these devices before. The actigraphs used are small and unobtrusive, and can provide a reliable and valid estimate of children's moderate-to-vigorous physical activity.⁶⁶⁻⁷⁰ Accelerometer data will be categorized into time spent in sedentary, as well as light, moderate, and vigorous activity using calibration thresholds specifically for children.^{69,71,72} The Physical Activity Checklist Interview,⁷³⁻⁷⁵ will be used to complement actigraphy data with descriptive self-reported assessments of physical activity.

Behavioral and psychosocial measures. Energy intake will be assessed by *Automated Self-Administered 24-Hour Dietary Recall* (ASA24-Kids, <http://appliedresearch.cancer.gov/tools/instruments/asa24/>), which is a validated web-based free method of a 24h dietary recall for children 10 y and older which will be performed at two time points around study visits 0, 18, 36 and 54 wk. At 0, 18 and 36 wk subject's parents will furthermore complete the *Child Eating Behavior Questionnaire* (CEBQ),⁷⁶ or the Adult Eating Behavior Questionnaire (AEBQ) which measures positive and negative eating behaviors (food responsiveness, enjoyment of food, emotional overeating, desire to drink, satiety responsiveness, slowness in eating, emotional undereating and fussiness) and the *Hyperphagia Questionnaire*⁷⁷, a 13- item questionnaire developed for use in patients with Prader-Willi syndrome but that has also been used to study hyperphagic behavior in other populations.⁷⁸⁻⁸⁰ These are all validated questionnaires and we have used them in previous studies.

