3a: Test GLP1RA treatment on energy homeostasis. Sample: All available EE and energy intake measures from DLW analyses and ASA24 dietary recalls at 0 and 36 wk will be included in the analyses (see Fig. 1). Tertiary outcomes analysis: The tertiary outcomes are change in EE and energy intake from baseline to 36 wk. Separate analyses will be conducted for EE and energy intake. For example for EE, an ANCOVA will be used to model the outcome of change in EE from baseline to 36 wk post-treatment with treatment as the factor of interest and Δ BMI and Δ energy intake included as covariates as both might affect EE independently of drug. A similar ANCOVA will be used to model the outcome of change in energy intake from baseline to 36 wk. Exploratory analyses will examine the change of energy intake after 6 and 18 wk of treatment to estimate effect sizes and inform the design of future studies.

Sample size and power: Assuming a normal distribution of differences, a type I error of 0.05, and a dropout rate of up to 20%, a final evaluable sample size of 19 subjects per group will provide 85% power to detect relative changes (average change divided by the pooled standard deviation (SD) of the change) in EE in relation to energy intake or energy intake in relation to EE of approximately 1 between the two groups. Based on preliminary pooled data from Ambler¹¹⁴ and Eliakim¹¹⁵ et al., the observed

pooled SDs of EE per DLW measures were 162 kcal/d and 155 kcal/d, respectively. Assuming a moderate correlation between baseline and follow-up measures ($r=0.5$), this would correspond to detectable differences of one pooled SD, or 162 kcal/d and 155 kcal/d, respectively. Expected results and benchmarks for success (exploratory efficacy endpoints): We expect that GLP1RA will lead to increased EE adjusted for Δ BMI and Δ energy intake.

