Study Visits (SVs): After the initial screening visit, there will be 5 study visits (see overview and measures in **Fig. 1**) to assess adherence, drug safety, outcomes, and to distribute the drug or placebo. Hypoglycemia medications will be adjusted as needed. During the duration of the treatment, subjects with persistent abdominal pain and nausea/vomiting will discontinue study medication and be evaluated for acute pancreatitis and cholecystitis. In children, most adverse effects are mild GI effects that are transient.¹¹⁷ Subjects not tolerating their current dose will be discontinued from study at PI's discretion. Study medication will resume if and only if no significant adverse event is found and subjects concur. Subjects need to fast and refrain from exercise for ten hours prior to study visits for fasting blood draws. Physical exams including Tanner staging, and inspection of injection sites will be done at all visits (except no Tanner staging at 6 weeks visit). If a subject withdraws from the study or is withdrawn by an investigator for any reason, subjects will be asked to complete SV4 study procedures, not including the DEXA scan.

Other measures assessed at SVs (see Fig. 1):

- Questionnaires (eating, activity): SVs 1, 3, 4,
- 24h dietary recall-done the week prior to : SVs 1, 3, 4, 5
- Anthropometry: SVs 1, 2, 3, 4, 5
- Vital signs: SVs 1, 2, 3, 4, 5
- Actimetry: SVs 1, 3, 4
- Blood for metabolic outcomes: SVs 1, 3, 4, 5
- OGTT: SVs 1, 3, 4
- Energy intake at free buffet meal: SVs 1, 4
- Whole body DEXA in order to evaluate body composition: SVs 1, 4
- DLW energy balance assessment: SVs 1, 4
- ECGs: SVs 1, 3, 4, and 5
- Safety labs (electrolytes, CBC, lipase, amylase, glucose, ALT, AST, creatinine, hemoglobin A1c, and thyroid hormones): SVs 2, 3, 4, 5
 - Additional serum will be obtained at all sites and stored at a central location (SCRI Seattle) for future use (3 ml in case anti-exenatide antibodies will need to be assessed)
- CEA: SVs 3, 4, 5
- Calcitonin: SV 5
- MRI (if needed): SV 1

Weekly Contact: Research participants will be contacted weekly by telephone/email to assess for potential adverse events, concomitant medications, and compliance with dosing. Participants will also be reminded about their urine collections, diet recalls, and return of the accelerometer during these phone calls.

Visit Schedule:

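### Aim 3a does not list the outcome's own baseline value as a covariate, although it is collected: a minor, low-cost efficiency gain that should be specified without mixing it with the post-randomisation covariates

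*Combined protocol and SAP*

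**What the plan says.** All references are to the combined protocol and SAP. In section 4, Analysis, under 3a, the tertiary outcomes are the changes in EE and in energy intake from baseline to week 36, analysed separately. The EE model is an ANCOVA on the change, "with treatment as the factor of interest and Δ BMI and Δ energy intake included as covariates". Baseline EE is not named. For intake the text says only: "A similar ANCOVA will be used to model the outcome of change in energy intake from baseline to 36 wk". Its covariates are not itemised.

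The power paragraph under the same heading claims 85% power with 19 evaluable patients per group for a relative effect of about 1. It continues "Assuming a moderate correlation between baseline and follow-up measures" (r = 0.5), and concludes that "this would correspond to detectable differences of one pooled SD, or 162 kcal/d and 155 kcal/d, respectively". The paragraph closes under the label "Expected results and benchmarks for success (exploratory efficacy endpoints"; Table 1 lists both measures as tertiary.

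Both baselines will be in the database. Section 6 lists "DLW energy balance assessment: SVs 1, 4" and "24h dietary recall-done the week prior to : SVs 1, 3, 4, 5", and SV 1 is week 0. Section 4, Study Measures, adds that the recall is one "which will be performed at two time points around study visits 0, 18, 36 and 54 wk".

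**The concern.** When the outcome is a change score, its own baseline is usually the most useful covariate. It is fixed before randomisation and negatively correlated with the change through regression to the mean. Adjusting for it also removes the effect of chance baseline imbalance, which is a practical matter with about 38 evaluable patients. Here the listed covariates are both measured after randomisation, and the obvious pre-randomisation one is absent. At stake is precision in the only planned test of whether the drug raises EE, and some discretion over what a similar model for intake will contain.

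**Working it through.** **Inputs.** From the plan: two-sided alpha 0.05, equal allocation, 19 evaluable per group, effect of one SD of change, EE SDs of 162 and 155 kcal/d, r = 0.5. Assumed: equal SDs at baseline and week 36.

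**1. The plan's own figures.**
- SD of change = s√(2(1 − r)). At r = 0.5 this is s, so 162 and 155 kcal/d. The printed detectable differences are those of an unadjusted change score.
- Noncentrality = √(19/2) = 3.08 on 36 df, giving power of 85.1%. The stated 85% reproduces.

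**2. Baseline added, treatment-only model.**
- Residual variance given baseline = s²(1 − r²), against 2s²(1 − r) without it. The ratio is (1 + r)/2 = 0.75, a cut of 25%.
- Estimating the baseline slope costs a factor of about 1 + 1/34, so the treatment-effect variance ratio is 0.75 × 35/34 = 0.772, a cut of about 23%.
- Power for the same difference (35 df, averaged over chance baseline imbalance) is 92.6%. Ignoring the slope cost gives 93.3%.
- Detectable difference: 162 × √0.75 × √(35/34) = 142.3 kcal/d, and 155 × √0.75 × √(35/34) = 136.2 kcal/d.

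**3. Dependence on r** (values other than 0.5 are assumed; each row takes one SD of change at that r as the difference).

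| r | Cut in residual variance | Power with baseline |
|---|---|---|
| 0.3 | 35% | about 95.5% |
| 0.5 | 25% | 92.6% |
| 0.7 | 15% | 89.3% |
| 0.9 | 5% | 85.8% |
| 0.95 | 2.5% | 84.9% (no gain) |

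The plan gives neither r nor SD for energy intake, so nothing can be quantified there.

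**4. The planned model, with change in BMI and change in intake included.** The documents give no correlations, so these are scenarios. Each covariate is assumed to correlate k (0 to 0.5) with change in EE and c (−0.25 to +0.2) with baseline EE; the two covariates correlate ρ (0 to 0.3) with each other. Units are SDs of change, with r = 0.5.

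- *Precision.* With no drug effect on the covariates, adding baseline EE lowered the variance of the treatment estimate in every structure, by 13% to 46%, and by 77% in one extreme combination (k = 0.5, c = +0.2).
- *What is estimated.* At r = 0.5 baseline EE correlates −0.5 with the change. The slope on each covariate is k/(1 + ρ) before baseline is added and (k + 0.5c)/(1 + ρ − 2c²) after. If the drug shifts the covariates, a treatment coefficient of 1 becomes 1 + (slope before − slope after) × (sum of shifts).
 - k = 0.3, c = −0.2, ρ = 0.3, shifts −1.12 (the Table 3 effect on % change in BMI) and −1 (assumed, intake): slopes 0.3/1.3 = 0.231 and 0.2/1.22 = 0.164; coefficient 1 + 0.067 × (−2.12) = 0.86.
 - k = 0.3, c = +0.2, ρ = 0.09, shift −1.12 on BMI only: slopes 0.3/1.09 = 0.275 and 0.4/1.01 = 0.396; coefficient 1 + (−0.121) × (−1.12) = 1.14.
- *Power* (simulation, 20,000 trials per scenario, BMI shift −1.12, conditional effect before adding baseline held at 1 SD):

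| k, c | Shift in intake | Power before → after |
|---|---|---|
| 0.3, 0 | 0 | 77.9% → 89.5% |
| 0.3, 0 | −1 | 74.0% → 85.6% |
| 0.3, −0.2 | 0 | 78.3% → 78.2% |
| 0.3, −0.2 | −0.5 | 78.2% → 76.2% |
| 0.3, −0.2 | −1 | 73.7% → 68.3% |
| 0.5, −0.25 | −0.5 | 89.1% → 86.0% |
| 0.5, −0.25 | −1 | 86.0% → 80.2% |

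The changes run from a loss of about 6 points to a gain of about 12. These are results for the structures tried, not limits; a positive correlation of the covariates with baseline EE gives larger gains.

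**The case against.** The strongest reply is that the 25% belongs to a model the plan does not propose. Beside two post-randomisation covariates, adding baseline EE changes the coefficient as well as its precision. That stands. The plan expects lower BMI and lower calorie intake at the test meal (Aim 1, expected result), so drug effects on both covariates are plausible and the power losses above are not contrived. Calling the addition free of consequence for the planned model would be wrong.

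It is also fair that the EE model is introduced as an example and is not said to be exhaustive, that the intake omission is inferred, and that r = 0.5 is a planning assumption. An unadjusted change score is unbiased under randomisation.

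These points limit the concern without removing it. The EE covariate list is a complete sentence that names two covariates, and the printed detectable differences match a comparison without baseline adjustment. Baseline EE does appear in Aim 3b, but there it is a predictor of BMI response in a different model.

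**Conclusion.** The point holds as a minor efficiency improvement in a tertiary, exploratory analysis. Its firm size is the treatment-only result: a 25% cut in residual variance and power of about 92.6% instead of 85.1%, given r = 0.5, equal SDs and 19 per arm. No single figure is claimed for the planned model, and none for intake.

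A reader might infer three stronger things that the documents do not support:
- That Aim 3a is underpowered or its power statement wrong. The 85% reproduces for an unadjusted change score.
- That 25% is the gain in the planned EE model. That gain depends on correlations and drug effects the documents do not give.
- That Aims 1 and 2 share the omission. No claim is made there.

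**What to change.** Before unblinding, amend the Aim 3a text to:
- add baseline EE to the EE model, and baseline energy intake (mean of the week-0 recalls) to the intake model;
- list the intake model's covariates explicitly;
- report, for each outcome, the baseline-adjusted treatment effect without the post-randomisation covariates (for EE, change in BMI and change in energy intake) alongside the planned conditional model, so that the precision gain is not confused with a change in what is estimated.

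The cost is SAP wording, one degree of freedom per model and a little extra analysis. No new data are needed.
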